 $(\text{Dose increase date or Dose reduction date} - \text{Start date of treatment with axitinib}) / 30.4375$
  - Duration (months) of subsequent treatments =  
 $(\text{Date of end of subsequent treatment or of latest follow-up if not suspended} - \text{Date of start of subsequent treatment}) / 30.4375$ . In the case of several subsequent treatments per patient, proceed as follows: the duration in months of each of the subsequent treatments will be calculated (from the start date to the end date or last check if it continues). This will be done for all subsequent treatments and then proceed to make the sum per patient of all durations of subsequent treatments

- Progression-Free Survival (PFS, in months) =  
 (Date of Disease Progression on treatment with axitinib or death from any cause – Date of start of treatment with axitinib) / 30.4375  
 If there is no progression or death, the case is censored as  
 PFS (months) = (Date of latest follow-up – Date of start of treatment with axitinib) / 30.4375
- Time to progression (TTP, in months) =  
 (Date of Disease Progression – Date of start of treatment with axitinib) / 30.4375  
 If there is no progression, the case is censored as  
 TTP (months) = (Date of latest follow-up – Date of start of treatment with axitinib) / 30.4375
- Overall Survival (OS, in months) = (Date of death – Date of start of treatment with axitinib) / 30.4375  
 If death has not occurred, the case is censored as  
 Overall Survival (OS, in months) = (Date of latest follow-up – Date of start of treatment with axitinib) / 30.4375
- Overall Survival since the start of first-line treatment (OS, in months) = (Date of death – Date of start of first-line treatment) / 30.4375  
 If death has not occurred, the case is censored as  
 Overall Survival (OS, in months) = (Date of latest follow-up – Start date of first treatment) / 30.4375
- Patient subgroups
  - A-Long-term responders: comprising patients with PFS  $\geq 9$  months.
  - B-Refractory (primary): comprising patients with best response to treatment = PD. This date is collected in the CRF form “axitinib treatment”.
- MSKCC risk group (described in appendix 11.1.). It will be analysed “Before the beginning of the first line”. These calculations will be performed on patients who have data on all the variables involved (in the case of a patient who does not have data on all the variables but has > 2 factors, it will be classified in the “Poor” risk group.

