  - o The following analyzes will be carried out in the patient population depending on whether or not they have had subsequent treatment;
    - OS per group (LR vs RF).
    - OS per axitinib line (2 VS  $\geq 3$ ).
    - OS per group (LR vs RF) for patients with axitinib in line 2.
    - OS per group (LR vs RF) for patients with axitinib online  $\geq 3$ .
- Overall survival based on most recent subsequent treatment.

The following analyzes will be performed in this subpopulation of patients in the groups of patients who have had the 2 most common subsequent treatments:

- o OS
- o OS per group (LR vs RF)
- o OS per axitinib line
- o OS per group (LR vs RF) for patients with axitinib online 2
- o OS per group (LR vs RF) for patients with axitinib online  $\geq 3$
- To describe treatments received at progression. The treatments received in the cases of PD for first line, 2nd line etc ... it means, in the treatments previous to axitinib will be described. The analysis of post-axitinib treatments will be shown as explained in section 9.2 Statistical analysis.

The responses of the previous treatments to axitinib initiated by PD in the different registered lines will be presented.

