**Inferential analysis:**

When an inferential analysis is required, parametric tests will be used for continuous variables, and non-parametric tests will be used for ordinal, categorical or non-parametric variables. The hypothesis tests to be carried out will be two-tailed test in all cases with a significance level of 0.05. For variables that are not adjusted to a normal (or parametric) distribution, the Mann–Whitney U test (for unpaired data) or the Wilcoxon signed-rank test (for paired data) will be used. The Chi-squared test (or Fisher’s exact test when applicable) shall be used for analysing the contingency tables and for the comparison of proportions and/or frequency distributions.

Survival analyses shall be performed using the Kaplan-Meier method, providing the median, mean, 95% confidence intervals, as well as number of events and number of censored cases.

When it is necessary to compare survival functions, the log-rank test will be used.

The assumptions of normality and homoscedasticity of the variables for the use of parametric tests will be studied.

The level of significance in all the statistical inference tests will be  $\alpha=0.05$ , two-tailed.

Adjustment by multiple comparisons is not planned.

Estimates will be calculated with a 95% confidence level, the SPSS statistical analysis software package, V18.0 or later, will be used.

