### Secondary objectives

A descriptive analysis will be performed on all secondary objectives.

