### Other analyses

A descriptive analysis will be performed of all variables that do not cover any of the above objectives, and which have been recorded in the CRF.

Observations to the descriptive analyzes:

- **SUBSEQUENT TREATMENTS:** The section on subsequent treatments will be analyzed in patients who have indicated suspension of axitinib treatment.

And in this set, the number of lines after axitinib registered will be obtained on the total number of patients and on patients with Have you received any subsequent treatment? = Yes. On this set of patients, post-axitinib treatments will also be analyzed as follows:

- **First post-axitinib treatment:** the drug received, and the best response achieved will be analyzed if the treatment continues. If it does not continue, the reason for the discontinuation will be analyzed (specifying if there are other reasons).

- **Second line and after suspension with axitinib:** a list with the registered data of these treatments will be shown.

- **DOSE MODIFICATION:** It will be described how many patients have modified doses and how many modifications have been registered. In patients with modification, the following elements will be described:

- **Type of modification** (the variables included in the CRD will be analyzed. This analysis should not be confused with the definition included in section 7 definition of variables and objectives of this document).

- **The changes registered** will be ordered in order of occurrence (1st modification, 2nd modification ... until the last one), and for each order the following will be described: the type of modification, the new dose and the reasons for modification.

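### SAP 7.2 gives two different grouping rules for OS by subsequent drug and no rule for patients who had both drugs, so the medians shown depend on the reading and on drug order

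*SAP*

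**What the plan says.** In SAP 7.2, a block titled "Overall survival based on most recent subsequent treatment" lists five OS outputs: overall, by response group, by axitinib line, and by response group within line 2 and within line 3 or later. The sentence introducing them says they are run "in the groups of patients who have had the 2 most common subsequent treatments". It does not say which line counts or where a patient with both drugs goes.

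The SAP expects such patients. Section 7 has a rule beginning "In the case of several subsequent treatments per patient, proceed as follows", but it concerns only the summing of treatment durations. Section 9.2, under other analyses, describes the first post-axitinib treatment and says of later ones that "a list with the registered data of these treatments will be shown".

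OS runs from the start of axitinib: "Overall Survival (OS, in months) = (Date of death – Date of start of treatment with axitinib) / 30.4375". On the type of analysis, section 9.2 states "A descriptive analysis will be performed on all secondary objectives". Section 9.1 adds "When it is necessary to compare survival functions, the log-rank test will be used".

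**The concern.** The heading and the sentence below it define different groups. Because OS starts at axitinib, a patient reaches a second post-axitinib drug only by surviving long enough to start it. Grouping by last drug takes those survivors out of the earlier drug's group and adds them to the later drug's. Grouping by ever-had leaves them in the earlier group and adds them to the later one as well, so the groups overlap. Either way, membership depends partly on the outcome.

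At stake is how the two drugs' medians and curves look next to each other. A programmer could follow either sentence and produce different numbers from the same data. If one drug tends to be given first, the other could appear to go with longer survival merely because of its place in the sequence.

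**Working it through.** **1. The readings applied to the same patients.** X and Y are the two most common drugs and Z is any other. The last column is the rule proposed under the fix.

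| Sequence after axitinib | By last drug | By ever-had | By first drug |
|---|---|---|---|
| X only | X | X | X |
| X then Y | Y | X and Y | X |
| Y then X | X | X and Y | Y |
| X then Z | not shown | X | X |
| Z then Y | Y | Y | not shown |

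Which two drugs count as most common can itself change with the column used for counting.

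**2. No planned figure to reproduce.** The SAP expects about 60 patients overall. It gives no number for those treated after axitinib or for those who had both drugs. Everything below rests on assumptions that are not in the documents.

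**3. Main check: two drugs A and B with identical effect, no censoring.** OS = T0 + R.
- T0, time to the first subsequent drug: exponential, mean 9 months.
- R, survival from then: exponential, median m = 8, 12 or 18 months, the same for A and B.
- T1, time on the first drug: exponential, mean 6 months.
- A patient with R > T1 switches to the other drug with probability s = 0.3 or 0.6.
- A comes first in 50% or 80%.

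The share receiving both drugs is b = s × (1/6) / (1/6 + ln2/m). With m = 12, ln2/12 = 0.0578 and the ratio is 0.1667/0.2244 = 0.743. So b = 0.223 for s = 0.3 and 0.446 for s = 0.6.

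The mechanism, with A first in 80% and s = 0.6:
- Last drug B: 0.2 × 0.554 = 0.111 stayed on B and 0.8 × 0.446 = 0.357 arrived from A. So 0.357/0.468 = 76% of that group had to survive to a switch.
- Last drug A: 0.8 × 0.554 = 0.443 stayed and 0.2 × 0.446 = 0.089 arrived. So 0.089/0.532 = 17% had to survive to a switch.
- Ever-had: 0.446/(0.8 + 0.2 × 0.446) = 50% of group A and 0.446/(0.2 + 0.8 × 0.446) = 80% of group B are also in the other group.

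Simulated median OS in months, A v B, 400,000 patients per row, A first in 80%:

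| m | s | First drug | Last drug (gap) | Ever-had (gap) |
|---|---|---|---|---|
| 8 | 0.3 | 17.2 v 17.2 | 16.5 v 18.8 (2.3) | 17.4 v 19.0 (1.6) |
| 8 | 0.6 | 17.1 v 17.3 | 15.5 v 19.4 (3.9) | 17.5 v 19.8 (2.3) |
| 12 | 0.3 | 21.7 v 21.7 | 20.7 v 23.6 (2.9) | 21.9 v 23.9 (2.0) |
| 12 | 0.6 | 21.6 v 21.6 | 19.2 v 24.3 (5.1) | 22.1 v 24.7 (2.6) |
| 18 | 0.3 | 27.9 v 27.7 | 26.7 v 30.1 (3.4) | 28.2 v 30.4 (2.2) |
| 18 | 0.6 | 27.8 v 27.7 | 24.8 v 30.8 (6.0) | 28.4 v 31.2 (2.8) |

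With A first in 50%, no gap appears under any rule, but the level still moves. At m = 12 and s = 0.6, both drugs show 21.6 by first or last drug and 23.1 by ever-had.

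**4. Second set-up, allowing a third drug.** Axitinib stops at 3 months in one third of patients and at 9 months plus an exponential with mean 10 in the rest. Later survival has median 12 months for every drug. A second drug comes after 1 month plus an exponential with median 6, for 70% of those still alive.
- X/Y first in 60%/20%: 26.6 v 26.7 by first drug, 24.7 v 28.4 by last drug (gap 3.7), 27.9 v 29.8 by ever-had (gap 1.9). About 18-21% of patients are in both groups.
- X/Y first in 50%/30%: the last-drug gap falls to 1.8-2.4 months, depending on how the second drug is drawn.
- X/Y equally likely to come first: 26.2 v 26.3.

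The gap shrinks towards zero as the order evens out.

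**5. If a log-rank test of drug against drug were added.** With two-sided alpha 0.05, m = 12, A first in 80% and s = 0.6, false positives by last drug are 10.3%, 12.9% and 15.2% at N = 30, 40 and 60. By first drug they are 5.9%, 6.3% and 5.3%. With s = 0.3 there is no clear inflation: 6.5%, 7.7% and 6.5% by last drug against 6.6%, 7.1% and 6.7% by first drug.

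**The case against.** A reader might infer that the SAP plans a comparison of the two drugs, and that its log-rank test is invalid because the groups overlap. The documents do not support that. None of the five outputs sets one drug against the other. The listed splits, by response group and by axitinib line, are disjoint within any drug group. Secondary objectives are descriptive, and the log-rank test is reserved for cases where a comparison is needed. The test figures above therefore apply only if someone adds that test.

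It is also tempting to read the first-treatment table in SAP 9.2 as a third, conflicting rule. It is a different table and defines no OS groups.

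The words most recent may be a translation slip for most common; the SAP has other traces of translation and defines no last-drug variable. If so, the last-drug gap falls away. The ever-had overlap and the missing rule for both-drug patients remain.

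The sizes rest on invented inputs, and drug order drives them. The sequence the SAP names as most observed puts one drug directly after axitinib. That makes unequal order plausible but does not establish it.

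Finally, noise is large. If 30 to 50 patients are treated after axitinib (an assumption), the difference in medians under first-drug grouping has an SD of about 8-11 months. That argues against reading much into these medians at all, but it does not justify leaving the grouping undefined.

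Protocol 7.2 does not list OS by subsequent drug, which limits the weight of the point.

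**Conclusion.** The inconsistency is on the page. Heading and text give different groups, and both-drug patients, whom the SAP expects, have no stated place. Either literal reading makes membership depend on surviving to a further line.

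Under the assumed inputs, with equal drugs and one given first more often, the false gap is about 1 to 6 months by last drug and about 1 to 3 months by ever-had. It is about zero when both are equally likely to come first. First-drug grouping leaves at most 0.2 months, which is simulation noise. None of these sizes comes from the documents.

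The consequence is limited to descriptive medians and curves in an exploratory secondary analysis. It is still worth correcting, because the correction is short and the current text allows more than one answer from the same data.

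**What to change.** Replace the heading and its rule with one mutually exclusive definition, for example: *Overall survival by first post-axitinib treatment. Each patient is assigned once, to the first drug started after axitinib. The two most frequent first drugs are shown. Later drugs do not change the group.*

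Report how many patients received both drugs. State that OS counted from axitinib start still includes the survival time before the subsequent drug began, or also show OS from the start of that drug. First-drug grouping removes the order artefact between drugs but not that time.

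The cost is SAP wording and programming only: the CRF already records drug, line and start date for each subsequent treatment. The drawback is a smaller second group, since patients who had that drug only as a later line no longer count there. In the main check with m = 12, A first in 80% and s = 0.6, drug B's group falls from 0.2 + 0.8 × 0.446 = 56% of treated patients by ever-had to 20% by first drug.

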**- Subpopulation of special interest**

Patients with the sunitinib and axitinib sequence, without liver or bone metastases and MSKCC risk group at the beginning of favorable or intermediate axitinib will be analyzed.

In this group of patients, the following analyzes will be carried out by group (long responders / refractories):

- Best response to treatment (RC, RP, EE, PE).
- Duration of treatment with axitinib (months).
- PFS, PFS will be shown in all patients of this subpopulation, and this same SLP per group
- TRO, clinical benefit.
- Time to progression.
- Overall Survival. OS will be shown in all patients of this subpopulation, and OS per group.

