## 5. MILESTONES

In order to obtain enough information to perform a proper analysis of the data, the proposed work plan is as follows:

Once the study is approved by the competent authorities and the contracts have been signed at each site, each study site will be opened and the investigator may start recording the requested data in the electronic case report form.

Before including the patient in the study, the investigator should review and verify the inclusion/exclusion criteria.

The observation period—given that it is an observational, retrospective study—will always be prior to the inclusion of the patient in the study, with this starting at the time of diagnosis of the study condition (renal cell carcinoma) and ending at the time of inclusion in the study, or the death of the patient if this occurs first.

[figure not shown]
The person appointed by the sponsor to monitor the study may request a face-to-face or remote visit from the site for the review of the data reported in the eCRF at any time after the first patient is included.

The site undertakes to fill in the data in the CRFs, and to resolve any discrepancies that may arise in them, on a regular basis and without interfering with the study’s planned schedule.

The study sponsor will regularly inform the investigators involved in the study on its status by sending electronic monitoring reports.

The administrative procedures for the study with the central IEC and the AEMPS are expected to start in September/October 2017, so the following schedule is being considered:

Milestone	Expected date
Date of approval from the central IEC	7 NOVEMBER 2017
Start of data collection Date of opening of the first site and start of study recruitment	15 MARCH 2018
End of recruitment period Expected date of study recruitment closure	30 SEPTEMBER 2018
End of data collection	30 DECEMBER 2018

Expected date of closing of study data collection	
Final results report Expected date for the final results of the study	31 MARCH 2019

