## 7. HYPOTHESIS AND OBJECTIVES

### 7.1. Primary objective:

- To describe the baseline clinical characteristics of the population of patients who are long-term responders to axitinib and to identify clinical factors associated with a long-term response to axitinib.

*For the study, “long-term responders to axitinib” has been defined as patients with progression-free survival [PFS] of at least 9 months with the drug, and “patients refractory to axitinib” has been defined as patients with disease progression in the first assessment after the start of treatment [estimated PFS  $\leq$ 3 months]*

To meet the study objective, two groups of patients with extreme response to the drug will be compared: a group of patients with long-term responses to the drug (group of long-term responders to axitinib) compared to a group of patients with disease progression in the first assessment after starting treatment (group of patients refractory to axitinib), in which the association of the following clinical factors will be analysed with the benefit of the treatment;

- Age ( $\leq$ 65 years and  $>$ 65 years)
- Baseline ECOG/PS at the start of treatment for each line (0, 1 and  $\geq$ 2)
- Number of previous treatment lines (1, 2 and  $\geq$ 3)
- Previous nephrectomy (yes and no)
- MSKCC risk group (favourable, intermediate and poor)
- IMDC risk group (favourable, intermediate and poor)
- Change in the MSKCC or the IMDC risk group with respect to the previous line (yes vs no);
- Histology (100% clear cells, main component of clear cells, main component of non-clear cells, 100% non-clear cells).

- Duration of first-line with a TKI ( $\geq 12$  months,  $\leq 6$  months;  $\leq 3$  months)
- Better response with the TKI received in first-line (CR/PR, SD, DP)
- Number of metastatic locations (1, 2 and  $\geq 3$ );
- Site of metastases (CNS metastases [yes vs no]; lymph nodes [yes vs no]; lung [yes vs no]; liver [yes vs no]; bone [yes vs no])
- Baseline LDH levels  $\leq 1.5 \times \text{ULN}$  (yes vs no)
- Baseline Hgb levels  $> \text{LLN}$  (yes vs no)
- Baseline corrected  $\text{Ca}^{++}$  levels  $\leq 10$  mg/dl (yes vs no)
- Baseline neutrophil levels  $\leq \text{ULN}$  (yes vs no)
- Baseline platelet levels  $\leq \text{ULN}$  (yes vs no)
- Neutrophil/lymphocyte ratio  $\leq 3$  (yes vs no)
- Smoking habits (smoker, non-smoker or ex-smoker)

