### **8.7. Data Analysis**

The data will be analysed using descriptive statistics. A statistical summary will be provided including sample size, mean, standard deviation, median and range for the continuous variables, when applicable; frequency and percentages for the categorical variables. Depending on the results of interest, a stratified data analysis may be conducted. Additional exploratory analyses will be conducted, if necessary.

Details of the methodology for the summary and statistical analysis of the data collected in this study will be documented in the Statistical Analysis Plan (SAP), which will be prepared, filed and maintained by the sponsor. The SAP can modify the plans originally described in the protocol; any major change in the definitions of the study’s primary objective or analyses will be reflected as an amendment to the protocol.

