## 1 AMENDMENTS TO PREVIOUS VERSIONS

This is version 3 of the SAP.

Amendment No.	Date	Summary of change(s)	Reason(s)
1	9 August 2018	
 
- Insertion of definitions and explanations for statistical analysis.
 
- Specification of methodology and analysis to be performed.
 
- Update of author and dates.
 
	Review of the first version of the SAP.
2	24 October 2019	
 
-Insertion of statistical analysis details, about the sob-groups of patients.
 
Specifications of methodology and analysis to be perform.
 
	Review after draft of results.

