- Duration of first-line treatment:([0-3] months, [3-6] months, [6-9] months, [9-12] months,  $\geq 12$  months).
- Duration of first-line treatment: ( $\leq 9$ months,  $>9$  months).
- Duration of first-line treatment: ( $\leq 12$ months,  $>12$  months).
- Duration of first-line TKi treatment: ([0-3] months, [3-6] months, [6-9] months, [9-12] months,  $\geq 12$  months).

It will be calculated the duration of the first line, if the drug was only a TKi.

- Duration of first-line TKi treatment: ( $\leq 9$ months,  $>9$  months).
- Duration of first-line TKi treatment: ( $\leq 12$ months,  $>12$  months).
- Duration of the first TKI treatment:( [0-3] months, [3-6] months, [6-9] months, [9-12] months,  $\geq 12$  months).

It will be calculated the duration of the first treatment with a TKi, in 1st or later line (always after axitinib).

- Patients treated with a TKi previous to axitinib other than first. It will be analysed the number of patients with a TKi previous to axitinib, different from the first TKi received.

It will be analysed the duration of this treatment.

- Best response with the TKI received in the first-line (CR, PR, SD, DP)
- Best response with a TKi previous to axitinib with a TKi other than first line (CR, PR, SD, PD).
- Best response with line prior to axitinib with a TKI if a line prior to axitinib other than the first one has been received (CR/PR, SD, DP).
- Number of metastatic locations (1, 2 and  $\geq 3$ ); See this definition in section 7 Definitions of variables and objectives.
- Site of metastases (CNS metastases [yes vs no]; lymph nodes [yes vs no]; lung [yes vs no]; liver [yes vs no]; bone [yes vs no]). In addition to showing the descriptive and comparative table of metastatic locations between groups, another similar table will be shown but with the categories “Hepatic” and “Bone” united in a single.
- Neutrophil/lymphocyte ratio  $\leq 3$  (yes vs no). See this definition in section 7 Definitions of variables and objectives. It will be analysed in all moments included in the study.
- Line of treatment in which it was received.

- 
- Presence of comorbidities.
  - Suspension of treatment.
  - Have you received any further treatment?
  - Has there been disease progression?
  - Best response to treatment (RC, RP, EE, PE).
  - Best response to treatment (RC / RP, EE, PE).
  - Duration of axitinib treatment.
  - Vital status

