It will be calculated as follows: Progression Free Survival to sunitinib (SLP, in months) = (Date of Progression of the Disease to treatment with sunitinib - Start date of treatment with sunitinib) / 30,4375. If there is no progression, the case is censored in SLP (months) = (Start date of treatment with axitinib - Start date of treatment with sunitinib) / 30,4375.

- **Majority sequence**

The number of patients receiving the second-line treatment will be shown, following the sequence that is most observed in all the patients included (SUT-AXI-NIVO).

The following analyzes will be carried out by group (long responders / refractories):

- Best treatment response (CR, PR, SD, DP).
- Duration of treatment (months).
- Progression-free survival. PFS will be shown in all patients with sunitinib-axitinib sequence and PFS per group.
- Objective response rate (ORR) and clinical benefit.
- Time to Progression
- Overall Survival. OS will be shown in all patients with sunitinib-axitinib sequence and OS per group
- Overall Survival since the beginning of 1st line. OS will be shown in all patients with sunitinib-axitinib sequence and OS per group

It is defined as: Global Survival from the beginning of the first line (SG, in months) = (Exit date - Start date of first line treatment) / 30,4375. If there is no exitus the case is censored in Global Survival (SG, in months) = (Date of last control - Start date of the first treatment) / 30,4375.

- To describe the duration of treatment with axitinib. It will be described as it is described in section 7. Definition of variables and objectives
- To describe the percentage of patients who had increase the dose of axitinib above 5 mg twice daily. It will be described as it is described in section 7. Definition of variables and objectives
- To describe the percentage of patients who had reduce the dose of axitinib below 5 mg twice daily. It will be described as it is described in section 7. Definition of variables and objectives
- To describe the tolerability of axitinib (see point 9.2. Statistical analyses, Safety objectives).
- To describe the response to treatments received at progression. The treatments received will be described in cases of DP for first-line, 2nd line, etc.; that is, in treatments prior to axitinib.
- Overall survival based on post treatment
  - o Overall survival. The OS will be displayed according to having received further treatment (Yes vs. No).

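### The subpopulation of special interest was very probably defined after draft results were seen, and SAP 7.2 reports it with no post hoc mark and no comparison with the remaining patients

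*SAP*

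**What the plan says.** - **Amendment log (SAP section 1).** Amendment 2, dated 24 October 2019, is described as "Insertion of statistical analysis details, about the sob-groups of patients", together with further specification of methods. The reason given is "Review after draft of results". Amendment 1 is dated 9 August 2018 and its entry does not mention subgroups.
- **Subpopulation of special interest (SAP 7.2).** It is defined as "Patients with the sunitinib and axitinib sequence, without liver or bone metastases and MSKCC risk group at the beginning of favorable or intermediate axitinib". PFS and OS are to be shown for the whole subpopulation and by response group. Best response, treatment duration, response rate, clinical benefit and time to progression are listed by response group.
- **Majority sequence (SAP 7.2).** Second-line patients are analysed "following the sequence that is most observed in all the patients included (SUT-AXI-NIVO").
- **Metastatic sites (SAP 7.1).** Besides the table of separate sites, "another similar table will be shown but with the categories" for liver and bone merged into one.
- **Protocol 7.1.** Liver, bone and MSKCC group appear only as separate factors (for the sites: "liver [yes vs no]; bone [yes vs no"]). No combination of them is named there, in Protocol 7.2 or in the SAP's own objectives (2.2). The SAP table list (section 10) has no entry for the subpopulation.
- **General wording.** Protocol 8.5 calls the study exploratory. Protocol 8.7 states "Depending on the results of interest, a stratified data analysis may be conducted". SAP 9.2 makes the secondary objectives descriptive, and SAP section 4 plans no multiplicity adjustment.

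**The concern.** Absence of liver or bone metastases and non-poor MSKCC risk are the favourable levels of factors that SAP 7.1 tests against long response in the same patients. Combining such levels after looking at results, and then describing outcome in the patients who remain, uses the same data to choose the subgroup and to estimate its outcome.

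The design makes this matter more. Only long responders (PFS of at least 9 months) and patients progressing at first assessment are enrolled, so PFS in any pooled subgroup depends mainly on its mix of the two. A choice that raises the long-responder share also raises the pooled PFS, and OS is likely to follow.

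At stake is what the study may conclude. A small subgroup, placed unmarked among the secondary objectives, could be read as a planned profile of patients who do well on axitinib.

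**Working it through.** The plan gives no power, event count or subgroup size to reproduce. The 60 patients are an expectation, and Protocol 8.5 says sample size calculations do not apply.

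**1. Timing.** Amendment 2 is the only log entry on subgroups, and its stated reason is the draft results. Its date falls about seven months after the planned final report (31 March 2019, Protocol section 5). Amendment 1 precedes the planned recruitment closure ("30 SEPTEMBER 2018"), so the commonest sequence among all included patients could not have been known then if recruitment ran to plan. The merged liver and bone table uses the same pairing that defines the subpopulation. Together these make a late origin very probable but do not itemise it.

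**2. Subgroup size.** Inputs:
- N = 60 (Protocol 8.5), at 2:1 (protocol abstract): 40 long responders, 20 refractory, share 40/60 = 66.7%.
- Liver and bone metastases 30-40% each (Protocol 6.1.1).
- Poor risk 23% (second-line series in SAP Appendix A1.3).
- Sunitinib first: not in the documents, assumed 60-80%.

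Size = 60 × P(sunitinib) × (1 − liver) × (1 − bone) × (1 − poor), assuming independence:
- Low: 60 × 0.60 × 0.60 × 0.60 × 0.77 = 10.0
- Middle: 60 × 0.70 × 0.65 × 0.65 × 0.77 = 13.7 (about 9 long responders, 5 refractory)
- High: 60 × 0.80 × 0.70 × 0.70 × 0.77 = 18.1

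**3. Optimism under a null.** In 20,000 simulated datasets per setting, no factor was related to outcome, so the true share is always 66.7%. The 23 candidates are the 19 items of Protocol 7.1 with the five sites counted singly (18 + 5).

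| How the restrictions were chosen | Mean long-responder share | Optimism (points) | Mean size |
|---|---|---|---|
| Four fixed in advance | 66.7% | 0 | 13.7 |
| Same four, each kept only where it looked favourable | 73.0% | 6.3 | 32.9 |
| Best 4 of 6 | 73.9% | 7.2 | 14.8 |
| Best 4 of 10 | 79.8% | 13.1 | 14.6 |
| Best 4 of 20 | 85.1% | 18.4 | 14.0 |
| Best 4 of 23 | 85.8% | 19.1 | 14.0 |

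The second row has a larger mean size because restrictions that did not look favourable are dropped. In the best-of rows each candidate keeps 60-80% of patients. Even with restrictions fixed in advance, the central 95% of simulated shares runs from 43% to 90%.

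**4. From share to PFS.** Suppose every refractory patient progresses before any long responder, and ignore censoring. With share s above one half, the pooled median PFS is then the (s − 0.5)/s quantile of PFS among long responders:
- s = 0.667: 0.167/0.667 = 0.25
- s = 0.730: 0.230/0.730 = 0.32
- s = 0.858: 0.358/0.858 = 0.42

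The pooled median thus moves from the 25th to the 32nd or 42nd percentile of the long responders' PFS with no real effect of any factor.

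**The case against.** Much of the case on the other side stands.

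- **Timing is inferred.** The log does not say that this subpopulation came in with amendment 2. In this SAP the word subgroups also denotes long responders versus refractory patients (section 5.2). The majority-sequence wording is the strongest dating evidence; the subpopulation itself carries none.
- **A reader might infer that the levels were picked because they did well.** No passage says so. MSKCC risk is an established model, and liver and bone are protocol-listed factors. If prior knowledge alone set the levels, there is no selection optimism.
- **A reader might take sunitinib first as another favourable level.** The documents do not show this. Protocol 6.1.6 cites a median axitinib PFS of 4.8 months after sunitinib against 12.1 months after cytokines, and prior sunitinib is part of the authorised indication (Protocol 6.1.4).
- **The other groupings work differently.** The majority sequence is chosen by frequency, not outcome. The merged liver and bone table is additional and replaces nothing.
- **Outputs by response group** are not moved directly by the long-responder share. The arithmetic bears on the pooled PFS and, less directly, OS.
- **The plan is exploratory and descriptive**, it allows result-dependent stratification, and its log openly discloses the timing. The subpopulation text itself specifies no test.

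The last point does not settle the matter. Wording that covers the whole study cannot show which analyses followed sight of results, and permission to stratify does not remove the need to label. A reader of the results will not have the amendment log beside the subgroup. The visible protocol gives no rationale for the combination, but section 6.2 contains a redaction, so I place no weight on that absence.

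**Conclusion.** The point holds as one of labelling and interpretation. SAP 7.2 presents a small subgroup of about 14 patients (10 to 18) that was very probably introduced after draft results, with no post hoc mark, no stated basis for its levels and no complement.

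Whether its results are optimistic depends on how the levels were chosen, which the documents do not say. The optimism in long-responder share is 0 points from prior knowledge alone, about 6 if four restrictions were kept only where favourable, and up to about 19 if they were the best four of 23. A reader might infer that the subgroup is certain to be optimistic, or by close to 20 points. The documents do not support either reading: the upper end needs a search rule that is recorded nowhere.

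These figures assume 60 patients at 2:1, independent factors, and the background prevalences and sunitinib share stated above. They show direction and rough size only. The main comparison of long responders with refractory patients is not affected.

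**What to change.** In SAP 7.1 and 7.2 and in the report:

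1. Mark the subpopulation of special interest, the majority sequence, the merged liver and bone table and any other amendment 2 addition as post hoc and hypothesis-generating. Itemise in the amendment log what was added.
2. State how the levels defining the subpopulation were chosen, and whether draft outcomes had been seen.
3. Report the subpopulation only beside its complement, with the size of each, 95% confidence intervals and no P values.
4. Draw no predictive conclusion from it without independent data.

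A bootstrap correction for optimism would have to repeat the selection, so it is worth running only if the selection steps are documented. An invented rule would give a spurious correction.

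The cost is a few labels and sentences and one extra column in the affected tables. The downside is a less striking subgroup message.
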